4.9.7 Overall Survival

Overall survival is defined as the interval between the date of the first dose and the date of death from any cause. Patients who are known to be alive as of their last known status will be censored at their date of last contact. Patients who are lost to follow-up will be censored at the date the patient is last known to have been alive. The last confirmed alive date is the latest of the following: study visit date, telephone contact date, end of study last confirmed alive date, follow-up systemic (anticancer) therapy end date or start date (if ongoing or end date is missing), local or central radiologist scan date, or other date in the clinical database.

OS will be estimated and displayed for the all-treated population using Kaplan-Meier methods (SAS® PROC LIFETEST). A Kaplan-Meier plot will be presented.

4.9.8 Total Tumor Volume

Total tumor volume will be summarize if data are available.

4.9.9 Patients Receiving Transplant

The fraction of patients receiving HSCT following camidanlumab tesirine, and without any other anticancer therapy in between other than the therapies preparing for HSCT, will be summarized.

4.10 Health-Related Quality of Life (HRQoL) Questionnaires

Scoring of QoL data and methods for handling of missing items or missing assessments will be based on each questionnaire's scoring manual.

4.10.1 European Quality of life (EuroQol)-5 Dimensions-5 Levels (EQ-5D-5L)

EQ-5D-5L is designed as an international, standardized, generic instrument for describing and evaluating QoL. The EQ-5D-5L consists of two parts:

- The descriptive system: QoL is classified according to five dimensions: mobility, self care, usual activities, pain/discomfort, and anxiety/depression. Each dimension comprises five levels of perceived problems (e.g., none, slight, moderate, severe, extreme).
- The visual analog scale (VAS): patients are asked to indicate their health state today on a VAS with the endpoints labeled 'the best health you can imagine' (score 100) and 'the worst health you can imagine' (score 0). Patients are asked to mark an "X" on the VAS to indicate their own health and then to report the score in a text box. If there is a discrepancy between where the patient has placed the X and the number he/she has written in the box, the number in the box is to be entered in the CRF together with a comment indicating the discrepancy.

Individual dimension responses will be summarized at each scheduled assessment with frequency counts and percentage of patients.

Descriptive statistics (mean, standard deviation, median and range) of actual values and changes from baseline will be presented at each scheduled assessment for the EQ-VAS.

A change of 7 points in VAS from the baseline is considered minimally important difference (MID) (Pickard et al., 2007). Patients will be classified as improved/deteriorated based on the established MID, i.e., if at least one of the post-baseline scores improves/deteriorates by the magnitude of the MID compared to baseline score. Proportion of patients with improvement/deterioration will be summarized.

Completion rate of EQ-5D-5L will be calculated as the number of patients who complete at least one question of EQ-5D-5L (e.g., either in descriptive system or VAS) divided by the number of patients treated at a visit. Summary of completion rate at each visit will be presented.

Summary analyses will include data up to the start of subsequent anticancer therapy/procedure.

A data listing for each individual dimension response, and the EQ-VAS will be presented for each patient at each visit.

4.10.2 Functional Assessment of Cancer Therapy - Lymphoma (FACT-Lym)

FACT-Lym is a lymphoma-specific subscale for the Functional Assessment of Cancer Therapy (FACT) questionnaire. It consists of 15 specific items that are used together with the core 27-item questionnaire FACT-G. The patient is asked to respond to each item with a score of 0–4, where 0 = not at all, 1 = a little bit, 2 = somewhat, 3 = quite a bit, and 4 = very much.

The FACT-Lym questionnaire includes subscales for physical well-being (PWB, 7 items), social/ family well-being (SWB, 7 items), emotional well-being (EWB, 6 items), functional well-being (FWB, 7 items) and additional concerns (Lymphoma Subscale, LymS, 15 items). The FACT-Lym scoring guide identifies those negatively stated items that must be reversed before being added to obtain subscale totals. Negatively stated items are reversed by subtracting the response from “4”. After reversing proper items, all subscale items are summed to a total, which is the subscale score. For all FACT-Lym scales and symptom indices, the higher score is associated with the better quality of life. The scores in the following items need to be reversed:

- Physical well-being: all individual items
- Social/family well-being: none
- Emotional well-being: 5 individual items (except for the second item, “I am satisfied with how I am coping with my illness”)
- Functional well-being: none
- Additional concerns: all individual items

The subscale scores will be a summation of each individual item score. If $\leq 50\%$ of item scores are missing, the subscale score will be calculated by multiplying the sum of the item scores by the number of items in the subscale, then divided by the number of non-missing item scores. This imputes the missing scores by the mean of the non-missing scores within a subscale.

Prorated subscale score = [sum of item scores] x [N of items in subscale]/ [N of items answered]

The following composite scores will be derived from the above subscale total scores:

- FACT_Lym Trial Outcome Index (TOI, score range: 0-116) = PWB + FWB + LymS
- FACT_G Total Score (score range: 0-108) = PWB + SWB + EWB + FWB
- FACT_Lym Total Score (score range: 0-168) = PWB + SWB + EWB + FWB + LymS

The TOI, FACT-G, and FACT-Lym Total scores will be set to missing if 20% or more of the included items are missing (eg, only calculated if at least 22 of 27 FACT-G items are completed) or any of the component subscales are missing.

The mean and mean change from baseline to each subsequent assessment will be summarized for the subscale and composite scores. The best change from baseline during the study, defined as the highest positive value among all post-baseline visits minus the baseline value, will also be summarized.

A change of 3 points for LymS and FACT-G Total Score, 6 points for FACT-Lym TOI, and 7 points for FACT-Lym Total score are considered MID ([Carter et al., 2008](#), [Kimberly et al., 2003](#)). Patients will be classified as improved/deteriorated based on the established MID for each measure. Proportion of patients with improvement/deterioration will be summarized.

Completion rate of FACT-Lym will be calculated as the number of patients with scores to calculate at least FACT-Lym TOI or FACT-G Total Score or FACT-Lym Total Score divided by the number of patients treated at a visit. Summary of completion rate at each visit will be presented.

Summary analyses will include data up to the start of subsequent anticancer therapy/procedure.

A data listing for each individual item, the subscale scores and the composite scores will be presented for each subject at each visit.

5 Interim Analyses

No formal interim analysis is planned.

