Characterize additional efficacy endpoints of camidanlumab tesirine	 DOR defined as the time from the first documentation of tumor response to disease progression or death CR rate defined as the percentage of treated patients with a best overall response (BOR) of CR Relapse-free survival (RFS) defined as the time from the documentation of CR to disease progression or death Progression-free survival (PFS) defined as the time from first dose of study drug until the first date of either disease progression or death due to any cause Overall survival (OS) defined as the time from first dose of study drug until death due to any cause Fraction of patients receiving hematopoietic stem cell transplant (HSCT).
Characterize the safety profile of camidanlumab tesirine	 Frequency and severity of AEs and SAEs Changes from Baseline of safety laboratory values, vital signs, Eastern Cooperative Oncology Group (ECOG) performance status, and 12-lead electrocardiograms (ECGs)
Characterize the PK profile of camidanlumab tesirine	 Concentrations and PK parameters of camidanlumab tesirine total antibody, PBD-conjugated antibody, and unconjugated warhead SG3199
Evaluate the immunogenicity of camidanlumab tesirine	• Frequency of confirmed positive anti-drug antibody (ADA) responses, their associated ADA titers and, if applicable, neutralizing activity to camidanlumab tesirine after treatment with camidanlumab tesirine

Objectives	Endpoints
Evaluate the impact of camidanlumab tesirine treatment on health-related quality of life (HRQoL)	 Change from Baseline in HRQoL as measured by EuroQoL-5 Dimensions – 5 Levels (EQ-5D-5L) and Functional Assessment of Cancer Therapy – Lymphoma (FACT-Lym)
Exploratory	
Assess the pharmacodynamic effects of camidanlumab tesirine	• Changes in levels of immunologically relevant biomarkers in blood such as but not limited to IL-2, IL-10, and soluble CD25 (sCD25)
Characterize tumor and tumor-associated non-tumor cells (TANT), as well as immunological relevant parameters in tumor tissue	 Measurement of CD25(+) tumor cells and TANT in baseline tumor tissue Measurement of tumor infiltrating lymphocytes (TILs) and other immunologically relevant parameters in baseline tumor tissue

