4.2.3 End of Treatment

An EOT visit should be performed as soon as possible after the decision to discontinue the study drug, preferably within 30 days after last dose of study drug, and before initiation of any new anticancer treatment.

When EOT coincides with a scheduled visit, the scheduled visit will become EOT.

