3.3 Modifications to the statistical section of the protocol

NA.

4 Statistical methods

All analyses use SAS® version 9.4 or higher. All available data will be used in the analyses, and important data will be included in data listings, sorted by patient, and by visit within patient. Missing data will not be imputed, except via censoring in survival analyses and as otherwise specified.

Unless otherwise noted, categorical data will be presented using counts and percentages, with the number of patients in the analysis population as the denominator for percentages. Percentages will be rounded to one decimal place, except 100% will be displayed without any decimal places and percentages will not be displayed for zero counts. Continuous data, unless otherwise noted, will be summarized using the number of observations (n), mean, standard deviation (std), median, minimum, and maximum. Minima and maxima will be rounded to the precision of the original value, and means, medians, and 95% confidence intervals (CIs) if presented will be rounded to 1 decimal place greater than the precision of the original value. The std will be rounded to 2 decimal places greater than the precision of the original value, up to a maximum of 3 decimal places.

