8.1 General conventions

8.1.1 Missing data

Handling of missing/partial dates

In general, imputation of missing dates will be made for AE onset date, AE resolution date, date of death, medication start/end dates, start and end dates of prior and subsequent therapies, and date of initial diagnosis for reporting. No imputation should be done at the data level.

- If dates are completely missing, no imputation will be made.
- For any partial date with missing year, no imputation will be made.
- For missing initial diagnosis date, if only day is missing, then the 1st of the month will be used; if only year is present, then Jan 1st will be used. If such imputed date for initial diagnosis is on or after date of first dose, then date of first dose - 1 will be used.
- If the imputed date is for an AE start date and is in the same year and month as but before the first dose date, then the first dose date will be used, or if the imputed AE start date is after the AE end date, then the AE end date will be used. If the imputed date is for an AE start date and is in the same year and month as but after the last dose date + 30 days, then the last dose date + 30 days will be used.
- If a medication date or time is missing or partially missing, so it cannot be determined whether it was taken prior or concomitantly, it will be considered as a prior and concomitant medication.
- If the imputed date is for a date of death and is before the last date that the patient is known to be alive, the latter date will be used.
- If the date part is missing for new anticancer therapy, the month and year will be used for comparison with disease assessment.

Handling of missing relationship to investigational product of TEAEs

If the assessment of the relationship to IP is missing, then the relationship to IP has to be assumed and the TEAE considered as such in the frequency tables of possibly related TEAEs, but no imputation should be done at the data level.

No other imputation of values for missing data will be performed.

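### By-cycle HRQoL means follow only patients still attending cycle visits, and the completion rate does not show the falling coverage

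*SAP*

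**What the plan says.** Protocol Table 2 makes HRQoL a secondary endpoint: "Change from Baseline in HRQoL as measured by" EQ-5D-5L and FACT-Lym. Protocol Table 1 schedules the questionnaires on Day 1 of each cycle and at EOT, with none in follow-up. Protocol Section 4.2.3 adds: "When EOT coincides with a scheduled visit, the scheduled visit will become EOT".

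SAP Section 4.10.2 summarises FACT-Lym as follows: "The mean and mean change from baseline to each subsequent assessment will be summarized for the subscale and composite scores". SAP Section 4.10.1 does the same for EQ-VAS: "Descriptive statistics (mean, standard deviation, median and range) of actual values and changes from baseline will be presented at each scheduled assessment". For both instruments the completion rate is a count of completers "divided by the number of patients treated at a visit". HRQoL summaries stop at the start of subsequent anticancer therapy.

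On missing data, SAP Section 4 states: "Missing data will not be imputed, except via censoring in survival analyses and as otherwise specified". SAP Section 8.1.1 closes with: "No other imputation of values for missing data will be performed". SAP Section 4.10 leaves missing items and missing assessments to the scoring manuals, and Section 4.10.2 itself gives rules only for missing items and subscales. No longitudinal model, display by time of dropout, or missing-data sensitivity analysis is planned for HRQoL.

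**The concern.** The cycle means describe a shrinking group. Protocol Section 5.5.1 requires study drug to stop for progression and for unacceptable toxicity, and Protocol Section 1.3 reports that TEAEs led 26% of Phase 1 cHL patients to stop. If such patients score worse, each later mean is taken over a better-scoring remainder. The score that would show the decline is recorded, but under EOT rather than in the cycle sequence.

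The completion rate would normally warn the reader, but its denominator shrinks together with its numerator. At stake is the secondary objective on the impact of treatment on HRQoL. A flat or rising trend could reflect who stayed rather than how patients fared.

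**Working it through.** The plan gives no HRQoL standard deviation, slope, exit rate or retention figure, so there is no plan figure to reproduce. The first two steps rest on the text and arithmetic. The others use assumed inputs.

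**1. Where a leaver's score goes.** Table 1 has separate columns for cycle visits and EOT. Protocol 4.2.3 turns a scheduled visit into EOT when the two coincide. SAP 4.10.1 and 4.10.2 summarise by assessment. Taken together, EOT scores form their own row. The SAP does not say so in words; this is an inference.

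**2. Completion.** Assume that 90% of patients treated at a visit complete the form and that 80, 60, 40 and 20 of 100 patients remain on drug. The SAP rate is 0.90 × remaining / remaining = 90% at every visit. Coverage of all treated patients is 0.90 × remaining / 100.

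| Remaining of 100 | SAP rate | Coverage of all treated |
|---|---|---|
| 80 | 90% | 72% |
| 60 | 90% | 54% |
| 40 | 90% | 36% |
| 20 | 90% | 18% |

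This needs no assumption about why patients leave. At EOT nobody need be treated, so the denominator is unclear.

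**3. Mean change, by strength of the score-exit link.** Assumptions: higher scores are better (as in SAP 4.10.2); each patient's change is slope × (cycle − 1), with slopes of mean −0.8 and SD 1.5 points per cycle; the exit probability per cycle is 10% at zero change, and its log-odds rise by a fixed amount for each point the score falls. The leaving visit is not counted in the cycle row. The all-patient mean is −0.8 × 4 = −3.2 at Cycle 5 and −0.8 × 8 = −6.4 at Cycle 9.

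| Log-odds per point | Exit odds multiplied for a 10-point fall | Cycle 9 mean of those remaining | Bias against −6.4 |
|---|---|---|---|
| 0 | exp(0) = 1.0 | about −6.4 | 0 |
| 0.02 | exp(0.2) = 1.2 | −5.0 | +1.4 |
| 0.05 | exp(0.5) = 1.6 | −2.7 | +3.7 |
| 0.15 | exp(1.5) = 4.5 | +3.3 (28% remaining) | +9.7 |

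At Cycle 5 the bias is smaller: −2.7 − (−3.2) = 0.5 at 0.05 per point, and −1.4 − (−3.2) = 1.8 at 0.15. For scale, the SAP's minimally important difference (MID) is 3 points for LymS and FACT-G and 7 for FACT-Lym Total and EQ-VAS.

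**4. Transplant exits.** A second illustration used a mean slope of −0.5, a 12% base exit probability and log-odds of 0.8 per 7 points. Its all-patient mean at Cycle 8 is −3.5 and its observed mean +4.0, a bias of +7.5. If patients improved by 7 points or more also leave for HSCT from Cycle 4, at 10% or 30% per cycle, the bias falls to +6.0 or +3.6. If HSCT at 30% per cycle is the only selective exit, the bias is −2.7.

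**5. Whether a model helps.** In a simulated run with a strong link, the Cycle 9 all-patient mean was −6.3. The planned by-visit mean gave +3.6, a repeated-measures model without EOT scores gave −3.4, and the same model with EOT scores placed by time gave −6.3. Full recovery is to be expected only where leaving depends on recorded scores.

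**The case against.** The strongest reply is that the plan already shows who left. SAP Section 4 reports n with continuous summaries, Section 4.7.1 tabulates patients dosed at each cycle, Section 4.2 tabulates reasons for stopping, and HRQoL data are listed by patient and visit. This stands. A reader might infer that attrition is concealed; the documents do not support that. What is missing is a completion rate that reflects it.

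Nor do the HRQoL analyses speak only for patients still on drug, as a reader might also infer. EOT is itself a scheduled assessment. The EQ-VAS improved/deteriorated classification counts any post-baseline score, and the FACT-Lym best change takes the highest score over all post-baseline visits, so EOT scores enter both. Neither repairs the cycle trend, and a best change favours good scores by construction.

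The direction is also open. Planned HSCT is a listed reason for stopping (Protocol 5.5.1), and step 4 shows that it can shrink or reverse the bias. The large figure in step 3 needs a strong link that nothing in the documents establishes.

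Finally, HRQoL is descriptive in this single-arm trial, and a repeated-measures model estimates a different quantity from an on-treatment mean. That stands too, and is why the model should be added beside the planned summary rather than replace it.

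**Conclusion.** The point holds in a conditional form. The completion denominator is explicit in the SAP, and its insensitivity to falling coverage is arithmetic. That cycle means cover only patients still attending follows from the schedule; the separate EOT row is a sound inference. Bias in the trend arises only if leaving is related to HRQoL, and its sign depends on which reasons for leaving dominate.

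The documents do not fix its size. Under the assumptions of step 3 the Cycle 9 bias is 0, about 1.4, about 4 or about 10 points as the link strengthens. A reader might infer from the last case that the trend will change sign; that needs the strongest link tried and a late cycle, and at 0.05 per point the observed mean is still negative. This is a worthwhile, inexpensive improvement to a secondary analysis. The primary ORR conclusion is unaffected.

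**What to change.** - Keep the planned by-visit means and label them as an on-treatment description.
- Add a mixed model for repeated measures for EQ-VAS and the FACT-Lym scores. Use all post-baseline scores up to new anticancer therapy, with baseline as covariate and each EOT score assigned to the cycle at which it falls.
- State that the model assumes missing at random and estimates the mean had patients remained under observation.
- Report completion also over patients expected at that time (treated, alive, no new therapy). At EOT, use patients who ended treatment.

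The cost is SAP wording and one extra model per score; no new data are collected. The downside is that missing at random cannot be tested.

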6 DSMB

When 15 patients completed one cycle of treatment, safety data will be summarized and individual listings presented for the independent Data and Safety Monitoring Board (iDSMB).

7 Final Analysis

For primary and key secondary endpoints analyses, a database snapshot will be taken when all patients who achieve PR or CR have a minimum of 12 months follow up after initial documented response (may be less for patients undergoing HSCT). All efficacy, safety, and PK endpoints will be analyzed and reported in the clinical study report (CSR).

The exact binomial test will be used in the final analyses for the primary endpoint because of the practical consideration that accrual cannot be limited to exactly 100 patients (≤ 110 patients expected). The table for number of responders needed to have 95% CI low bound of ORR $> 35\%$ is in section 9.4 of the study protocol.

Follow-up analyses will be performed when all the patients complete the study per protocol. The results will be reported in a CSR addendum.

8 Data handling conventions

8.1 General conventions

8.1.1 Missing data

Handling of missing/partial dates

In general, imputation of missing dates will be made for AE onset date, AE resolution date, date of death, medication start/end dates, start and end dates of prior and subsequent therapies, and date of initial diagnosis for reporting. No imputation should be done at the data level.

- If dates are completely missing, no imputation will be made.
- For any partial date with missing year, no imputation will be made.
- For missing initial diagnosis date, if only day is missing, then the 1st of the month will be used; if only year is present, then Jan 1st will be used. If such imputed date for initial diagnosis is on or after date of first dose, then date of first dose - 1 will be used.
- If the imputed date is for an AE start date and is in the same year and month as but before the first dose date, then the first dose date will be used, or if the imputed AE start date is after the AE end date, then the AE end date will be used. If the imputed date is for an AE start date and is in the same year and month as but after the last dose date + 30 days, then the last dose date + 30 days will be used.
- If a medication date or time is missing or partially missing, so it cannot be determined whether it was taken prior or concomitantly, it will be considered as a prior and concomitant medication.
- If the imputed date is for a date of death and is before the last date that the patient is known to be alive, the latter date will be used.
- If the date part is missing for new anticancer therapy, the month and year will be used for comparison with disease assessment.

Handling of missing relationship to investigational product of TEAEs

If the assessment of the relationship to IP is missing, then the relationship to IP has to be assumed and the TEAE considered as such in the frequency tables of possibly related TEAEs, but no imputation should be done at the data level.

No other imputation of values for missing data will be performed.

